4.3 ANALYSIS OF TREATMENT GROUP COMPARABILITY

For continuous variables, the mean, median, SD, minimum, and maximum will be calculated. For categorical variables, number and percentage in each category will be displayed. The units/categories to be used are indicated within the brackets and separated by commas.

Except where stated, all assessments of treatment group comparability will utilize the date of the baseline visit (not the date of the screening visit) as the reference point in time, unless otherwise stated. For Arm 4, the treatment baseline will be used when comparing to other arms.

Biomarker values for Arm 4 at pre-treatment baseline will be summarized separately and compared to Arm 1 baseline values.

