4.4 EFFICACY ANALYSIS

All biomarker assessments (scheduled or unscheduled) will be summarized after applying visit windows. Summary of the visit windowing rules can be found in Appendix 2. See Module 3 for full visit window specifications. If multiple values of the same parameter occur within the same time window for blood biomarkers

Ocrelizumab—Genentech, Inc.

15/Statistical Analysis Plan ML29966

or regular lab values, the worst value for that parameter will be presented in the summary table. If multiple MRI scans occur within the same time window, the scan closest to the scheduled visit date will be included in the analysis.

All summaries will be done based on the ITT population and summaries will be provided by the actual arm, as determined by the actual timing of 2nd LP:

For patients randomized to Arm 1-3,

If the second LP date is missing then patient is included in the arm where originally randomized to;

Else:

Study Day of second LP (= date of the 2nd LP – 1st infusion start date +1)	Treatment Arm
≤126	Arm 1
127-266	Arm 2
≥267	Arm 3

Patients randomized to Arm 4 will be summarized as Arm 4 regardless of the timing of 2nd LP.

Unless otherwise specified and where appropriate, statistical tests, if any, will be performed at the two-sided 5% significance level. Corresponding 95% confidence intervals will be presented as appropriate. No corrections for multiple testing will be applied.

For biomarkers measured below the lower limit of quantification (LLOQ), numeric values will be imputed using half of the LLOQ.

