4.4.2 Exploratory Endpoints

4.4.2.1 Summaries of Exploratory Endpoints Over Time

For RMS patients in Arm 4, values at pre-treatment baseline and treatment baseline, and change and percent change from treatment baseline to post-baseline visits will be summarized.

For RMS patients in arms 1-3 and PPMS patient arm, CSF biomarker endpoints, blood biomarker endpoints and MRI biomarker endpoints stated in Section 2.2.2 will be summarized over time following the same rule as the primary efficacy endpoint, as stated in Section 4.4.1. The median (IQR) value of CSF and blood biomarkers at pre-treatment baseline, treatment baseline and post-baseline visits will be plotted over time and color coded by each arm. Scatter points of data will be laid over the median (IQR) plot for blood NfL level, CD19+ B cell and CD3+ T cell numbers.

Mean (SD) of MRI biomarker endpoints will be summarized over time.

For blood biomarkers, patient arms will also be pooled to look at the effect of ocrelizumab over time.

4.4.2.2 Comparison between Arm 1 and Arm 4

For patients in Arm 4, changes from pre-treatment baseline to treatment baseline will be compared to Arm 1 change from treatment baseline to Week 12 through an ANCOVA model adjusting for baseline DMT status (DMT naïve vs. DMT experienced) and baseline biomarker level for the following endpoints:

- CSF CD19+ B cell, CD3+ T cell and NfL
- Blood CD19+ B cell, CD3+ T cell and NfL

If data are highly skewed, ANCOVA model will be based on percent changes.

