4.4.2.3 Associations Among Biomarker Data

The following associations will be assessed separately for each arm at each scheduled visit:

- CSF with blood NfL, CD19+ B cells, and CD3+ T cells.
- change in CSF NfL levels, CD19+ B cells, CD3+ T cells with changes in T1 Gd-enhanced lesions from treatment baseline to post-baseline scheduled visits for arms 1-3 patients, and from pre-treatment baseline to treatment baseline visit for arm 4 patients.

- brain volume with CSF NfL levels.
- change in CSF NfL levels with new/enlarging T2 Gd-enhanced lesions.
- blood NfL with CSF CD19+B cells, CD3+T cells.
- blood NfL with T1 Gd-enhanced lesions.
- change in blood NfL with new and/or enlarging T2 lesions.

The Spearman's rank correlation coefficient will be used to evaluate the relationship among the levels of biomarkers or between levels of biomarkers and clinical parameters. Baseline values across patient arms may be pooled when appropriate. Scatterplots of the two-by-two associations may also be constructed to aid in the interpretation of the coefficients.

The following associations will be assessed by Mann-Whitney test:

- Baseline CSF NfL in DMT-experienced patients versus DMT-naïve patients.
- Baseline CSF NfL levels in patients with 0, 1 and >1 baseline T1 Gd-enhanced lesions.
- Percent change in CSF NfL in patients having at least one relapse event versus patients without relapse during the study.
- Percent change in CSF NfL in DMT-experienced patients versus DMT-naïve patients.

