In the RMS cohort, 15 patients will be included in Arm 1 to explore the possible reduction in NfL at Week 12 post-treatment and 15 patients will be assigned to the delayed start RMS control arm (Arm 4). *At least 15 patients will be recruited to the PPMS cohort. The above sample sizes are not based on statistical considerations and are meant to help explore the changes in biomarkers and generate hypotheses for future studies.*

Based on the above, the total sample size for this study will be *at least* 96 patients. The sample size will be increased by approximately 10% in order to account for potential missing post-treatment CSF information; therefore, the number of patients to be enrolled in the RMS cohort will be 88 (Arm 1: 16 patients, Arm 2: 28 patients, Arm 3: 28 patients, and Arm 4: 16 patients), and *at least* 16 in the PPMS cohort. Therefore, the total number of patients to be enrolled is *at least* 104; *however, the addition of patients to the PPMS cohort would allow for even more detailed information on biomarkers.*

Interim Analyses

For the RMS patients, interim analysis may be performed when approximately 50% of patients have had their second LP. For the PPMS patients, interim analyses may be performed after approximately 50% of patients have had their baseline LP and/or approximately 50% have had their second LP.

APPENDIX 2
VISIT WINDOWING FOR MAIN TREATMENT AND LTE PERIOD

Visit window for vital sign and blood biomarkers (Arm 1-4 & PPMS):

Report Visit Label	Nominal study days (from baseline)	Visit window (in terms of study days from baseline)	Notes
Week -12 (Arm 4)	-84	< -14	
Baseline (Arm 1-3 & PPMS)	1	<=1	ANLFL for the record most close to day 1 if there are multiple records in the window
Baseline (Arm 4)	1	-14 - 1	Give two week window for baseline
Week 3	21	2<= and <=53	Window is from Day 2 until Week 7.5+0.5 day
Week 12	84	54<= and <=126	Window is from Week 7.5+1.5 day until Week 18
Week 24	168	127<= and <=210	Window is from Week 18+1 day until Week 30
Week 36	252	211<= and <=294	Window is from Week 30+1 day until Week 42
Week 48	336	295<= and <=350	Window is from Week 42+1 day until Week 50
Week 52	364	351 - < LTE Day 1 (if entered LTE) 351 – patient end of main study date (if not entered LTE)	Window is from Week 50+1 day until end of main study date
Week 96	672	LTE Day 1 - <=840	Window is from LTE Day 1 to Week 120
Week 144	1008	>=841 and <=1,176	Window is from Week 120+1 day until Week 168

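### SAP 4.4 presents the worst blood-biomarker value in a window, relapse samples included, while the Arm 1-3/PPMS blood baseline and MRI take the closest record; exploratory blood changes can therefore compare a selected extreme with a neutral baseline

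*SAP*

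**What the plan says.** SAP 4.4 opens with "All biomarker assessments (scheduled or unscheduled) will be summarized after applying visit windows". For blood biomarkers and regular laboratory values with several results in one window, "the worst value for that parameter will be presented in the summary table". The next sentence treats imaging differently: "If multiple MRI scans occur within the same time window, the scan closest to the scheduled visit date will be included in the analysis".

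The blood-biomarker table in SAP Appendix 2 adds a third rule, for the Arm 1-3 and PPMS baseline only: "ANLFL for the record most close to day 1 if there are multiple records in the window". The Arm 4 baseline row says only "Give two week window for baseline". Arm 4's Week -12 row and the post-baseline rows carry no selection note.

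The schedules in Protocol Appendices 1 to 3 mark serum, plasma and the blood cell panel in the unscheduled relapse-visit column. Protocol 6.4.2 plans to analyse unscheduled samples.

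Three planned analyses can draw on the selected values:

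- SAP 4.3: "Biomarker values for Arm 4 at pre-treatment baseline will be summarized separately and compared to Arm 1 baseline values".
- SAP 4.4.2.2, for blood as well as CSF markers: "changes from pre-treatment baseline to treatment baseline will be compared to Arm 1 change from treatment baseline to Week 12 through an ANCOVA model".
- SAP 4.4.2.3, correlations by arm at each scheduled visit, including "CSF with blood NfL, CD19+ B cells, and CD3+ T cells" and blood NfL with Gd-enhancing lesions.

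**The concern.** A worst-value rule suits safety laboratory data, where the aim is not to miss an abnormality. Applied to a change-from-baseline biomarker, it selects on the outcome. Protocol 1.1 says CSF NfL has been correlated with relapse, and the synopsis in the SAP says CSF and serum NfL are highly correlated. A relapse-visit blood NfL will therefore tend to be the higher of two values and will displace the scheduled one.

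In Arms 1-3, with high NfL read as worse, this tends to understate the fall on treatment. The Arm 1 versus Arm 4 contrast matters more, because Arm 4 is there so that regression to the mean is not reported as a drug effect. An extreme chosen as Arm 4's starting value would build in that very artefact. An extreme chosen as Arm 1's Week 12 value would hide a real fall. Both errors push the Arm 1 minus Arm 4 difference upward.

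Direction is a second gap. For CD3+ counts and pre-treatment CD19+ counts, worst could mean highest or lowest, and the two readings distort in opposite ways.

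The correlations raise a third issue. A worst blood value may come from a different date than the lumbar puncture or scan it is paired with, whereas footnote r of Protocol Appendix 1 wants blood cell samples on the same day as the CSF.

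**Working it through.** The plan states no figure that depends on this rule, so the check compares the rules, then the windows, then the size.

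**1. Rules side by side**

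| Data | Rule when a window holds several records |
|---|---|
| MRI, all visits (SAP 4.4) | closest to scheduled date |
| Blood, Arm 1-3/PPMS baseline (SAP Appendix 2) | closest to Day 1 |
| Blood, Arm 4 Week -12 and Baseline | none printed; SAP 4.4 worst value by default |
| Blood, all post-baseline windows | worst value |

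**2. Where the rule can act**

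Scheduled post-baseline blood visits in the Main Treatment Period are Days 15 ± 2, 84 ± 7, 168 ± 7, 252 ± 7, 336 ± 7 and 364 ± 7. Each falls in exactly one window, so the rule acts only on extra samples: relapse, repeat or early termination. The footnote that removes early-withdrawal and follow-up visits from windowing is printed only under the MRI and EDSS tables, and it does not name relapse visits.

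Window lengths (last day − first day + 1):

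- Week 3, Days 2-53: 52
- Week 12, Days 54-126: 73
- Week 24, Days 127-210: 84
- Week 36, Days 211-294: 84
- Week 48, Days 295-350: 56
- Week 52, Days 351-503: 153, assuming extension Day 1 is Day 504 (Week 72)
- Arm 4 Week -12, Days -84 to -15: 70 (nominal; the window has no lower bound and the visit allows ± 7 days)
- Arm 4 Baseline, Days -14 to 1: 16, counting Day 0
- Extension: Day 504-840 = 337; 841-1,176 = 336; 1,177-1,512 = 336; then 1,513 onward

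**3. Effect of one substitution**

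One substituted record moves an arm's mean change by (difference between the two records)/n: 1/16 = 6.3% of that difference in Arms 1 and 4, and 1/28 = 3.6% in Arms 2 and 3.

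**4. Expected shift for a patient with two values**

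Assume two normal values with equal SD and correlation ρ. Taking the higher adds SD × √((1 − ρ)/π). The plan gives ρ = 0.6 for CSF NfL; using it for blood is an assumption.

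- ρ = 0.6: √(0.4/π) = 0.36 SD (0.47 at ρ = 0.3; 0.18 at ρ = 0.9).
- Reading worst as high rather than low doubles this, to 0.71 SD at ρ = 0.6.
- If relapse raises the extra value by b = 1 SD (assumed), the shift is bΦ(b/s) + sφ(b/s) with s = √(2 × 0.4) = 0.894, which gives 1.06 SD.

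**5. How often**

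Protocol 1.2.1.2 gives Phase II annualized relapse rates of 0.125 on ocrelizumab 300 mg × 2 (0.086 and 0.186 over other periods), 0.364 on interferon and 0.637 on placebo. Assume they carry over.

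- Arm 1, Week 12 window: 16 × 73/365 = 3.2 patient-years. Expected relapses are 3.2 × 0.125 = 0.4 (0.3 to 0.6), or 2.5% of patients. The mean shift is 0.025 × 0.36 = 0.009 SD, or 0.025 × 1.06 = 0.026 SD with the 1 SD rise.
- Arm 4, Week -12 window: 16 × 70/365 = 3.07 patient-years. Expected relapses are 1.1 at 0.364 and 2.0 at 0.637, or 7% to 12% of patients. At 12.2% the starting value rises by 0.122 × 0.36 = 0.044 SD, or 0.122 × 1.06 = 0.129 SD.

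In an unadjusted comparison of changes the two add: 0.009 + 0.044 = 0.05 SD to 0.026 + 0.129 = 0.16 SD. The ANCOVA adjusts for baseline, so the Arm 4 part carries a weight of about ρ: 0.009 + 0.6 × 0.044 = 0.04 SD to 0.026 + 0.6 × 0.129 = 0.10 SD. A simulation with no drug effect gave a bias of 0.00 SD under closest-record selection.

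**6. What is untouched**

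The powered figure rests on CSF NfL. SD of change = √(780² + 310² − 2 × 0.6 × 780 × 310) = 643.7, and n = 51 gives paired-t power of 0.802. The worst-value rule does not enter.

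**The case against.** The strongest reply is one of scope and size. All three primary endpoints are in CSF, the analyses are mostly descriptive, the median (IQR) plots resist single extremes, and on ocrelizumab fewer than one relapse is expected in Arm 1's Week 12 window. In Arms 1-3 the error for NfL is also conservative. All of that stands. It limits the priority but does not justify the rule.

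Several stronger readings are tempting, and the documents do not support them:

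- *That the SAP leaves the direction of worst undefined altogether.* SAP 4.4 refers to Module 3 for full window specifications, and Module 3 was not supplied. It may give a direction or an Arm 4 baseline rule. It would not remove the worst-value rule printed in 4.4 or its conflict with the MRI and baseline rules.
- *That the direction matters greatly for CD19+ on treatment.* Protocol 5.1.1.1.4 describes depletion by 14 days, sustained through treatment, and SAP 4.4 sets values below quantification to half the limit. Two on-treatment values will usually both sit near the floor, so the 0.71 SD figure does not apply to them.
- *That the Arm 1 versus Arm 4 ANCOVA uses worst values.* The rule is worded for the summary table. Which record enters the model or the correlations is not stated.
- *That Arm 4's starting value will be a relapse extreme.* Footnote b of Protocol Appendix 2 ties the relapse visit to relapses after both lumbar punctures, while Protocol 3.1 sets no such limit. On the footnote's reading, only the Arm 1 part remains.
- *That the missing rule for two CSF values in one window is a defect.* Module 3 may hold it.

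**Conclusion.** The concern holds for exploratory blood biomarkers. The printed rule selects on outcome after baseline, conflicts with the neutral rules for MRI and for the Arm 1-3/PPMS baseline, and gives Arm 4 no closest-record rule in the supplied text. It should be fixed, though it is not critical.

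The documents do not fix its size, because they give no rate of extra samples. Under the relapse-rate assumptions above, the shift in Arm 1's Week 12 mean is about 0.01 to 0.03 SD. The Arm 1 versus Arm 4 bias reaches about 0.10 SD in the ANCOVA (0.16 SD unadjusted) only if Arm 4 relapses at the placebo rate, pre-treatment relapse visits take place, relapse adds 1 SD, and the worst record enters the model. Repeat or early-termination samples could add to this.

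The extension windows may be more exposed because they run for 336 days or more, but the supplied documents do not show how often blood is drawn there. A reader might infer that the primary results or the sample size are in doubt; they are not, since both rest on CSF.

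**What to change.** In SAP 4.4:

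1. For blood biomarkers, replace the worst value with the record closest to the scheduled visit date, preferring the scheduled visit, at every timepoint and in every arm. Include Arm 4's Week -12 and Baseline rows and the extension windows, and state a tie-break.
2. State that this same record is used in the summaries and in the 4.4.2.2 ANCOVA.
3. For blood-CSF and blood-MRI correlations, use the blood record taken on the same day as the paired lumbar puncture or scan, or closest to it. The record closest to schedule need not be the same-day one, because CSF may be taken up to 7 business days before dosing.
4. Keep worst value for safety laboratory parameters only, with a direction for each.
5. Continue to report relapse-visit blood values, identified as such, for example as marked points on the planned scatter overlay. The relapse subgroup summary in SAP 4.4.4 covers only the CSF primary endpoints, so relapse values in blood would otherwise go unseen.

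Before programming, reconcile the Week 3 target day (nominal day 21 in SAP Appendix 2, Day 15 in Protocol Appendix 1). Also reconcile Protocol 3.1 with footnote b of Protocol Appendix 2 on relapse visits in Arm 4.

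The cost is SAP wording and a programming flag; no new data are needed.

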4.4.1 Primary Endpoints

For RMS cohort arm 1-3, the following values at treatment baseline and post-baseline visits, and changes and percent changes from treatment baseline to post-baseline visits will be summarized by arm:

- Levels of NfL in CSF
- Number of CD19 + B cells in CSF
- Number of CD3+T cells in CSF

The median (IQR) value at pre-treatment baseline, treatment baseline and post-baseline visits will be plotted over time and color coded by each arm. Scatter points of data will be laid over the median (IQR) plot.

4.4.2 Exploratory Endpoints

4.4.2.1 Summaries of Exploratory Endpoints Over Time

For RMS patients in Arm 4, values at pre-treatment baseline and treatment baseline, and change and percent change from treatment baseline to post-baseline visits will be summarized.

For RMS patients in arms 1-3 and PPMS patient arm, CSF biomarker endpoints, blood biomarker endpoints and MRI biomarker endpoints stated in Section 2.2.2 will be summarized over time following the same rule as the primary efficacy endpoint, as stated in Section 4.4.1. The median (IQR) value of CSF and blood biomarkers at pre-treatment baseline, treatment baseline and post-baseline visits will be plotted over time and color coded by each arm. Scatter points of data will be laid over the median (IQR) plot for blood NfL level, CD19+ B cell and CD3+ T cell numbers.

Mean (SD) of MRI biomarker endpoints will be summarized over time.

For blood biomarkers, patient arms will also be pooled to look at the effect of ocrelizumab over time.

4.4.2.2 Comparison between Arm 1 and Arm 4

For patients in Arm 4, changes from pre-treatment baseline to treatment baseline will be compared to Arm 1 change from treatment baseline to Week 12 through an ANCOVA model adjusting for baseline DMT status (DMT naïve vs. DMT experienced) and baseline biomarker level for the following endpoints:

- CSF CD19+ B cell, CD3+ T cell and NfL
- Blood CD19+ B cell, CD3+ T cell and NfL

If data are highly skewed, ANCOVA model will be based on percent changes.

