1.2.1.2 Clinical Activity

Study WA25046 met its primary endpoint of confirmed disability progression (CDP) sustained for at least 12 weeks, showing that treatment with ocrelizumab significantly reduced the progression of clinical disability for 12 weeks compared with placebo (risk reduction: 24%; hazard ratio: 0.76; 95% confidence interval [CI]: 0.59–0.98; $p=0.0321$). The study also met its key secondary endpoints. Time to CDP sustained for 24 weeks was significantly ($p=0.0365$) reduced with ocrelizumab compared with placebo (risk reduction: 25%). Change in the 25-foot timed walk from baseline to Week 120 had a significantly ($p=0.0404$) reduction of 29% with ocrelizumab. Percent change in total volume of T2 lesions on MRI from baseline to Week 120 was significantly ($p<0.0001$) improved with ocrelizumab (decrease of 3.4%) compared with placebo (increase of 7.4%). Finally, percent change in whole brain volume from Week 24 to Week 120 was significantly ($p<0.0206$) improved with ocrelizumab (17.5% reduction) compared with placebo.

Study WA21493 results at Week 24 demonstrated that both doses of ocrelizumab achieved the primary endpoint by significantly reducing the number of Gd-enhancing lesions compared with placebo ($p<0.0001$). Both ocrelizumab dose groups showed statistically significant reductions in annualized relapse rate (ARR) compared with the placebo group (ARR=0.125 for the ocrelizumab 300 mg \times 2 group [$p=0.0005$] and ARR=0.169 for the ocrelizumab 1000 mg \times 2 group [$p=0.0014$]) compared with ARR=0.637 for the placebo group, representing a relative reduction (RR) of 80% and 73% in ARR versus placebo group for the low- and high-dose ocrelizumab groups, respectively. In exploratory analyses, both ocrelizumab groups were superior to the IFN- β -1a group for the primary endpoint ($p<0.0001$) and the 300 mg \times 2 group for ARR (ARR=0.364 for the IFN- β -1a group, representing an RR of 66% in ARR [$p=0.03$] for the ocrelizumab 300 mg \times 2 group versus the IFN- β -1a group and an RR of 53.6% in ARR [$p=0.086$] for the ocrelizumab 1000 mg \times 2 group versus the IFN- β -1a group) ([Kappos et al. 2011](#)).

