6.4.2 Exploratory Endpoints

Exploratory endpoints for the PPMS cohort include:

- *Change in levels of NfL in CSF from treatment baseline to post-treatment with ocrelizumab*
- *Change in number of CD19+ B cells in CSF from treatment baseline to post-treatment with ocrelizumab*
- *Change in number of CD3+ T cells in CSF from treatment baseline to post-treatment with ocrelizumab*

CSF biomarker endpoints for both cohorts may include, but may not be limited to:

- Activation markers, functional attributes, activity, and/or molecular status of cells (e.g., proteins, non-heritable RNA levels, etc.) at *all collected timepoints* before and after treatment with ocrelizumab, *including optional samples*
- Levels of soluble neurodegeneration markers and/or inflammatory markers at *all collected timepoints* before and after treatment with ocrelizumab, *including optional samples*

Blood biomarker endpoints for both cohorts may include, but may not be limited to:

- Change in number of CD19+ B and CD3+ T cells in blood at *all collected timepoints* before and after treatment with ocrelizumab, *including at unscheduled visits*
- Activation markers, functional attributes, activity, and/or molecular status of PBMCs or cell products (e.g., proteins, non-heritable RNA levels) at *all collected timepoints* before and after treatment with ocrelizumab, *including at unscheduled visits*
- Levels of NfL, levels of soluble neurodegeneration markers, and/or inflammatory markers in the peripheral blood serum or plasma at *all collected timepoints* before and after treatment with ocrelizumab, *including at unscheduled visits*

MRI biomarker endpoints for both cohorts may include, but may not be limited to:

- Total number of T1 Gd-enhanced lesions at *all collected timepoints* before and after treatment with ocrelizumab, *including at unscheduled visits*
- Change in total T2 lesion volume at *all collected timepoints* before and after treatment with ocrelizumab, *including at unscheduled visits*
- Total number of new and/or enlarging T2 lesions at *all collected timepoints* before and after treatment with ocrelizumab, *including at unscheduled visits*
- Changes in regional or total brain volume at *all collected timepoints* before and after treatment with ocrelizumab, *including at unscheduled visits*
- Total number of leptomeningeal-enhancing regions at *all collected timepoints* before and after treatment with ocrelizumab, *including at unscheduled visits*

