2.2.2 Exploratory Endpoints

The exploratory endpoints for RMS Arm 4 include:

Change from first LP to second LP comparing Arm 4 to Arm 1 in:

- Levels of NfL in CSF
- Number of CD19 + B cells in CSF

- Number of CD3 + T cells in CSF
- Levels of NfL in blood
- Number of CD19 + B cells in blood
- Number of CD3 + T cells in blood

The exploratory endpoints for the PPMS cohort are:

- Change in levels of NfL in CSF from treatment baseline to post-treatment
- Change in number of CD19 + B cells in CSF from treatment baseline to post-treatment
- Change in number of CD3+T cells in CSF from treatment baseline to post-treatment

For both RMS and PPMS cohorts, other exploratory endpoints include the impact of ocrelizumab treatment on other CSF biomarkers, blood biomarkers and MRI biomarkers listed in this section.

Change from treatment baseline in CSF biomarkers:

- %CD19+ B cell
- %CD3+ T cell
- %CD4+ (CD3+)
- CD4+CD3+ number
- %CD4- (CD3+)
- CD4-CD3+ number
- %IgD+CD27+ (CD19+)
- IgD+CD27+CD19+ number
- %IgD+CD27- (CD19+)
- IgD+CD27-CD19+ number
- %IgD-CD27- (CD19+)
- IgD-CD27-CD19+ number
- %IgD-CD27+ (CD19+)
- IgD-CD27+CD19+ number
- %CD138+CD38+ (IgD-CD27+)
- CD138+CD38+IgD-CD27+CD19+ number
- %CD138-CD38- (IgD-CD27+)
- CD138-CD38-IgD CD27+CD19+ number
- %CD138-CD38+ (IgD-CD27+)
- CD138-CD38+IgD-CD27+CD19+ number
- %CD38+ (IgD+CD27-)
- CD38+IgD+CD27-CD19+ number
- IgG
- IgM
- CXCL13
- CCL19
- Strem2

- YKL40
- IL-6

Change from treatment baseline in Blood biomarkers:

- %CD19+ B cell
- %CD3+ T cell
- CD3+ T cell number
- CD4+T cell number
- CD8+T cell number
- CD19+ B cell number
- CD56+CD16+ NK cell number
- CD4/CD8 Ratio
- NfL
- CXCL13
- IL-6

MRI biomarkers:

- Mean number of T1 Gd-enhanced lesions
- Mean number of new and/or enlarging T2 lesions
- Mean T2 lesion volume
- Mean Regional or total brain volume
- Mean number of leptomeningeal-enhancing regions

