Patients who complete the study and choose not to continue on ocrelizumab treatment, or who discontinue from treatment early, should enter the Safety Follow-up Period and be assessed every 24 weeks for 48 weeks counting from the date of the last infusion of ocrelizumab. After 48 weeks, if the peripheral blood B-cell count remains depleted, monitoring of the patient should continue at 24-week intervals until the B-cell count has returned to the baseline value or to the lower limit of the normal range, whichever is lower (see Appendix 8).

For patients who complete the study and continue to receive ocrelizumab, a Long-Term Extension of the study beginning at Week 72 will be conducted every 6 months for up to 4 years at the time of treatment infusion for as long as they continue to receive ocrelizumab (Appendix 9). A Long-Term Extension of the study is needed to understand the correlation between long-term changes in biomarker assessments with long-term safety and long-term efficacy of ocrelizumab. The Long-Term Extension extends the study to a total of 5 years, which is the necessary timeframe to investigate whether baseline CSF NfL levels may be prognostic for long-term brain atrophy as assessed by 5-year declines in whole brain volume in MS patients (Arrambide et al. 2016). CSF NfL and serum NfL levels are highly correlated in the disease (Disanto et al. 2017), and therefore measurement of blood NfL levels may allow for predictions of brain atrophy in MS patients. Treatment of MS patients with disease-modifying therapies has been demonstrated to cause short-term (6 months to 1 year) accelerations in whole brain-volume loss (pseudoatrophy) but slows long-term (3 – 5 years) brain atrophy (Zivadinov et al. 2008). Therefore, a Long-Term Extension is needed in order to accurately establish an association between serum NfL levels and brain atrophy in patients in the study.

Biomarkers will be monitored in a longitudinal fashion before and after treatment with ocrelizumab in order to assess dynamic changes in biomarkers as they relate to drug exposure, length of time on drug, response to drug, and MS disease pathogenesis. Biomarkers will be assessed via blood draws throughout the study and via LP in CSF at baseline before the first dose of ocrelizumab and at one other timepoint.

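### The only brain-volume change the SAP specifies runs from treatment baseline and may include early pseudoatrophy; a within-patient change from an on-treatment scan is worth adding

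*SAP*

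**What the plan says.** For Arms 1-3 and the PPMS cohort, SAP 4.4.2.1 states that "MRI biomarker endpoints stated in Section 2.2.2 will be summarized over time following the same rule as the primary efficacy endpoint". The rule it points to, in SAP 4.4.1, covers values at each visit and adds that "changes and percent changes from treatment baseline to post-baseline visits will be summarized by arm". For Arm 4, SAP 4.4.2.1 again has "change and percent change from treatment baseline to post-baseline visits will be summarized".

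Brain volume is among the MRI endpoints of SAP 2.2.2, worded as a level: "Mean Regional or total brain volume". SAP 4.4.2.1 also asks for the mean and SD of the MRI endpoints over time. Protocol 6.4.2 words the endpoint as a change, "Changes in regional or total brain volume at" every collected visit, and names no reference scan.

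The synopsis in SAP Appendix 1 says that disease-modifying therapies cause "short-term (6 months to 1 year) accelerations in whole brain-volume loss (pseudoatrophy") but slow atrophy over 3 to 5 years. It concludes: "Therefore, a Long-Term Extension is needed in order to accurately establish an association between serum NfL levels and brain atrophy". It also names 5-year declines in whole brain volume as the outcome for which baseline CSF NfL may be prognostic.

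Protocol 1.2.1.2 reports that the pivotal PPMS study assessed "percent change in whole brain volume from Week 24 to Week 120".

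**The concern.** The synopsis treats early brain-volume loss on treatment as partly something other than lasting atrophy, and the analysis section then measures change from the scan that precedes that loss. Longer follow-up, which is the synopsis's answer, dilutes a one-off early loss. It does not take that loss out of a change from baseline.

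Nothing else in the SAP text supplies a later reference. None is named in the endpoints (2.2.2), the summaries (4.4.2.1), the associations (4.4.2.3), the sensitivity analyses (4.4.3) or the MRI windows (Appendix 2). SAP 4.4.2.3 lists brain volume with CSF NfL, but as brain volume rather than a change from a stated scan. The Arm 1 versus Arm 4 comparison in 4.4.2.2 covers only NfL, CD19+ B cells and CD3+ T cells, so no planned untreated comparison shows what the early loss would have been.

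At stake is how the extension's brain-volume results are read. Its exploratory objectives include the impact of ocrelizumab on indices of neurodegeneration, and brain atrophy is central to its rationale. If the early acceleration occurs here, change from baseline will make tissue loss on treatment look larger than it is, most of all at Week 52.

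**Working it through.** The plan gives no expected value, SD or power for brain volume, so there is no figure to reproduce. What can be checked is timing, and then size under stated assumptions.

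**Inputs from the documents**

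- Scheduled MRI after treatment baseline in the Main Treatment Period: Weeks 12, 24 and 52 (days 84, 168 and 364; Protocol Appendices 1-3).
- MRI windows in the extension: Weeks 96, 144, 192 and 240 (SAP Appendix 2).
- The Final Analysis summarises Main Treatment Period data only (SAP 4.9).
- Pseudoatrophy period: 6 months to 1 year (SAP Appendix 1), taken as 24 and 52 weeks.

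**Step 1. Share of the baseline-to-visit interval inside the period.** For a visit at week w and a bound of b weeks, the share is min(b, w)/w.

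| Visit | 52-week bound | 24-week bound |
|---|---|---|
| Week 12 | 100% | 100% |
| Week 24 | 100% | 100% |
| Week 52 | 100% | 24/52 = 46% |
| Week 96 | 52/96 = 54% | 24/96 = 25% |
| Week 144 | 52/144 = 36% | 24/144 = 17% |
| Week 192 | 52/192 = 27% | 24/192 = 12.5% |
| Week 240 | 52/240 = 22% | 24/240 = 10% |

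At the 1-year bound, every scheduled-visit change in the Final Analysis is measured wholly inside the period.

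**Step 2. Other reference scans.** From Week 52, the share inside the first year is 0% at every extension visit. From Week 24, the interval to Week 52 lies outside the 6-month bound but wholly inside the 1-year bound; to Week 240 the share inside the first year is (52 - 24)/(240 - 24) = 28/216 = 13%. Follow-up to Week 240 is (240 - 52)/52 = 3.6 years from Week 52 and (240 - 24)/52 = 4.2 years from Week 24.

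**Step 3. Precision of the Week 52 reference.** The Week 52 MRI window opens at day 267, which is 364 - 267 = 97 days, about 14 weeks, before the nominal visit. SAP 4.4 takes the scan nearest the scheduled date when several fall in one window, but a lone early scan would still count as Week 52.

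**Step 4. Size, by assumption only.** None of these inputs is in the documents. Let underlying loss be a % per year, and let a one-off excess of x percentage points be complete by Week 52. After t years, the excess is x/(a·t + x) of the apparent loss, with t = 52 × 7/365.25 = 0.997 at Week 52 and 240 × 7/365.25 = 4.60 at Week 240.

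- a = 0.6, x = 0.1: 0.1/0.698 = 14% at Week 52; 0.1/2.86 = 3% at Week 240.
- a = 0.4, x = 0.3: 0.3/0.699 = 43%; 0.3/2.14 = 14%.
- a = 0.2, x = 0.5: 0.5/0.699 = 71%; 0.5/1.42 = 35%.

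In the middle case the apparent annual rate from baseline is 0.40 + 0.30/0.997 = 0.70% at Week 52 and 0.40 + 0.30/4.60 = 0.47% at Week 240, against 0.40% from a Week 52 reference. If the excess accrues evenly over 52 weeks, a Week 24 reference leaves 0.30 × 28/52 = 0.16 points. The rate from Week 24 to Week 52 is then still 0.40 + 0.16/0.537 = 0.70%, and to Week 240 it is 0.40 + 0.16/4.14 = 0.44%.

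**The case against.** The strongest reply is that the SAP does not set out to estimate an atrophy rate. In SAP 2.2.2 the CSF and blood lists are headed as changes from treatment baseline; the MRI list is not, and it asks for means. Mean brain volume at each visit will be shown, so the group course after Week 24 or Week 52 can be seen. The baseline change comes only from a general cross-reference. This stands in part. A reader might infer that the SAP plans an on-treatment atrophy estimate and that no display escapes the early loss; the documents support neither. But differences between visit means give no within-patient change and no SD, and the only change specified is from treatment baseline.

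Second, the synopsis already answers pseudoatrophy with longer follow-up, and its 5-year-decline aim runs naturally from baseline. That stands as a reason to keep the baseline change. It is tempting to make Week 24 the main reference and relegate baseline, but this would demote the display closest to that aim, and Week 24 may itself lie inside the stated period.

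Third, applicability is uncertain. The synopsis speaks of disease-modifying therapies in general and gives no size. RMS patients may enter already treated with such therapy. The protocol does not say why the pivotal PPMS study measured brain volume from Week 24, so a link to pseudoatrophy is inference; the same paragraph does report T2 lesion volume from baseline, which shows only that the later reference was not used for every MRI measure. All of this stands, and it limits the conclusion to a possible overstatement of unknown size.

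Last, the list of outputs is in SAP Module 2, which is not among the documents, so a re-baselined table cannot be ruled out. The SAP text does not call for one.

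**Conclusion.** The point holds as a modest, inexpensive improvement. The only brain-volume change the SAP text specifies is from treatment baseline, and by the SAP's own synopsis the first 6 months to 1 year on therapy may include accelerated loss that does not reflect long-term atrophy. At the 1-year bound this covers all scheduled post-baseline scans in the Final Analysis and about 22% of the interval to Week 240. The likely direction is to overstate tissue loss on treatment.

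The amount is not in the documents. The 14% to 71% at Week 52 and 3% to 35% at Week 240 depend entirely on assumed inputs (underlying loss 0.2 to 0.6% per year, excess 0.1 to 0.5 points) and show only that dilution by Week 240 is partial. A reader might infer a demonstrated bias of that size in this trial; the documents do not support that. The conclusion rests on the synopsis's general statement applying to ocrelizumab in these patients. Brain volume is an exploratory endpoint in a mostly descriptive study, and no primary result changes.

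**What to change.** In SAP 4.4.2.1:

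- Keep change and percent change from treatment baseline, and label the baseline-to-Week-52 change as possibly including pseudoatrophy.
- Add within-patient percent change in total and regional brain volume from the Week 52 scan to Weeks 96, 144, 192 and 240. Define the reference as the scan nearest day 364, and report how far each reference scan lies from that day.
- Add the same change from the Week 24 scan to Weeks 52 to 240, for comparability with the pivotal PPMS study, with a note that Weeks 24 to 52 may still lie in the pseudoatrophy period.

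No new scans are needed, because all these visits already have MRI windows in SAP Appendix 2. The cost is a few lines of text and one or two derived variables. Patients without the reference scan drop out of the added tables, so each table should state its number of patients. Follow-up from the reference is also shorter than from baseline.
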